11.3. CLINICAL LABORATORY EVALUATIONS

Laboratory tests will be performed at Screening and periodically throughout the clinical trial as described in the schedule of events, Section 4. Only data collected by the central laboratory will be included in the analyses with the exception of the screening safety data. Standard international units will be used for all summaries. Laboratory tests within each category and scheduled visit are given in Table 9.4.1. Data for all visits, scheduled or unscheduled, will be listed.

At least one laboratory measurement obtained subsequent to at least one dose of Study Treatment is required for inclusion in the analysis of each specific parameter. To assess change from baseline, a baseline or screening measurement is also required.

Table 11.3.2: Laboratory Tests and Scheduled Study Visits

Laboratory Category	Laboratory Tests Included	
Hematology	hemoglobin, hematocrit, red blood cell (RBC) count, RBC morphology, white blood cell (WBC) count with differential, mean corpuscular volume (MCV), mean corpuscular hemoglobin (MCH), mean corpuscular hemoglobin concentration (MCHC), and absolute platelet count.	
Chemistry	albumin, alkaline phosphatase (ALP), alanine aminotransferase (ALT; SGPT), aspartate aminotransferase (AST; SGOT), bilirubin (total and direct), blood urea nitrogen (BUN), calcium, carbon dioxide (CO2), chloride, creatinine, creatinine phosphokinase (CPK), glucose, phosphate, potassium, sodium, total protein, and uric acid.	
Urinalysis	bilirubin, glucose, ketones, blood, nitrite, pH, protein, specific gravity, and microscopy (if indicated by macroscopic findings).	
Other	Urine Pregnancy Test for Female Subjects	
Estimated Glomerular Filtration Rate (eGFR)	Adult population (≥ 18 years of age): eGFR will be calculated by the MDRD equation at baseline:	

Syneos Health #1009367

eGFR (mL/min/1.73 m2) = $175 \times (Scr)-1.154 \times (Age)-0.203 \times (0.742 \text{ if female}) \times (1.212 \text{ if African American}) \text{ (Levey 2009)}$	
Pediatric population (3 - < 18 years of age): eGFR will be calculated by the Schwartz equation at baseline:	
eGFR (mL/min/1.73 m ²) = $(0.41 \times \text{Height in cm})$ / Creatinine in mg/dL (Schwartz 2009)	

- Actual (observed) values and changes from baseline in hematology and clinical chemistry laboratory parameters will be summarized by treatment group at each scheduled visit
- The number and percentage of subjects with laboratory measurements outside of the normal range will also be summarized by treatment group and visit.
- Shift from Baseline at each post-Baseline visit will be provided by treatment group in a 3-by-3 contingency table. Denominators for percentages will be the number of subjects with non-missing data at the specific assessment and baseline.
- Box and Whiskers Plots by visit will be produced for all quantitative hematology and clinical chemistry parameters.
- Actual (observed) values in urinalysis and other laboratory parameters will be summarized by treatment group.
- The number and percentage of subjects with laboratory measurements outside of the normal range will also be summarized by treatment group and visit.
- Incidence of patients that have Potentially Clinically Significant (PCS) values at any post-baseline visit.

All data will be listed.

11.4. VITAL SIGNS

The following vital sign data will be collected at all study visits:

- Sitting Systolic Blood Pressure (SBP) (mmHg)
- Sitting Diastolic Blood Pressure (DBP) (mmHg)
- Heart Rate (beats/min)
- Respiratory Rate (breaths/min)
- Body Temperature (degree Celsius or Fahrenheit)
- Body Weight (kg)
- Height (cm)

Syneos Health #1009367

At least one vital sign measurement obtained subsequent to at least one dose of Study Treatment is required for inclusion in the analysis of each specific parameter. To assess change from baseline, a Baseline or screening measurement is also required.

For all parameters, actual (observed) values will be presented and summarized for all scheduled study visits by treatment and overall.

Vital signs data will be fully described using descriptive statistics. Actual values and change from baseline will be summarized.

Vital signs data will be summarized by parameter, visit and time point, treatment group and overall for all subjects in the SAF.

All vital signs data shall be listed chronologically by treatment group for subjects in the SAF.

11.5. ECG

Electrocardiograms (ECGs) will be read centrally and the following ECG parameters will be reported:

- Overall assessment of ECG (by central reader) will be tabulated:
 - Normal
 - o Abnormal, Not Clinically Significant
 - Abnormal, Clinically Significant.
 - The results will be included in a per patient listing.

ECG data, along with the date and time of assessment, will be listed for all subjects in the SAF population. Any clinically significant ECG/ Holter results may be recorded as an AE.

ECG data will be classified as "Normal", "Abnormal, Not Clinically Significant" or "Abnormal, Clinically Significant".

ECG data will be summarized by visit, and by treatment group and overall for all subjects in the SAF population. Summary tables will show the number and percentage of subjects with normal, abnormal non-clinically significant (NCS) or abnormal clinically significant (CS) findings at each visit.

Shift tables for ECG result to each study visit on treatment will be provided. Subjects with both a non-missing baseline and at least one non-missing post-baseline finding will be included in the shift table.

ECG data will also be listed chronologically for all subjects in the SAF.

Syneos Health #1009367

11.6. PHYSICAL EXAMINATION

A physical examination will be performed according to the Schedule of Assessments described in Section 4. Body systems findings will be classified as "Normal" or "Abnormal" and abnormalities are described. Any physical examination findings are reported as medical history or adverse events.

Physical examination findings will be fully summarized using the frequency and percentage of subjects under each classification for each body system with an indication as to whether the finding is clinically significant. Summary tables will be sorted by parameter, visit/time point and treatment group, and overall, for all subjects in the SS.

Results from physical examinations will be listed chronologically for all subjects in the SAF population.

11.7. DERMATOLOGY EXAMINATION

A full dermatological examination will be performed according to the Schedule of Assessments described in Section 3.8 and will comprise of the dermatological examination of the following body systems: Scalp and Hair, Face, Neck, Chest and Abdomen, Back, Arms, Hands and Fingernails, Legs, Feet and Toenails and Other. Any clinically significant dermatological examination results may be recorded as an AE.

Body systems will be classified as "Normal" or "Abnormal" and abnormalities are described.

Dermatological examination findings will be fully summarized using the frequency and percentage of subjects under each classification for each body system. Summary tables will be sorted by parameter, visit/time point and treatment group, and overall, for all subjects in the SS.

Syneos Health #1009367

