4 STUDY POPULATION SELECTION

4.1 Inclusion Criteria

Subjects meeting all the following criteria will be considered eligible for study entry:

- 1. Subject is aged 3 years or older.
- 2. Subject has a genetically-confirmed diagnosis of SLS.
- 3. Subject has active ichthyosis that is Grade 2 or higher on the VIIS scaling severity score.
- 4. Subject or subject's caretaker is willing and able to provide written informed consent prior to the initiation of any study procedures. Assent will be solicited from pediatric subjects capable of providing assent.
- 5. Females of child-bearing potential: Negative pregnancy test at Screening and Baseline Visits.
- 6. Subjects who are sexually active agree to use medically acceptable method (as defined by the Investigator) of birth control as follows:
 - For females: Compliant with a contraceptive regimen if of child-bearing potential during the study, or documented to be surgically sterile or post-menopausal.
 - For males: Compliant with a contraceptive regimen during the study or documented to be surgically sterile.

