10.5 Safety Analyses

10.5.1 Adverse Events

The assessment of safety will be determined from dermatological endpoints, vital sign measurements, physical examinations, hematology and chemistry laboratory testing, ECG readings, use of concomitant medications, and review of adverse events.

The SAP will contain mock tables for all safety relevant information which will be produced for each study part and over the entire study.

Safety tables will contain by treatment and combined treatments information concerning AEs, TEAEs, SAEs, unexpected AEs and clinical safety laboratory values. Treatment and vehicle group safety narratives will be written. If required a safety narrative will be written for selected subjects. AEs, TEAEs, unexpected AEs and SAEs will be coded according to the Medical dictionary for Regulatory Activities (MedDRA) preferred terms. Tables variously organized by preferred terms, system organ class, treatment emergence, treatment relationship, severity and study termination will be presented for AEs, TEAEs, unexpected AEs and SAEs.

Descriptive statistics will be presented by treatment and time for safety laboratory values or in change tables for categorized lab variables (e.g., normal vs. abnormal, present vs. absent). Other safety information (e.g., normality of dermatological endpoints, normality of vital signs, normality of physical examinations, normality of ECG outcomes, concomitant medication usage) will be summarized in tables and medically evaluated.

If inferential analysis for any safety variable seems appropriate, the comparison will be made using an appropriate statistical test and designated as *post-hoc*.

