5.7. ADMINISTRATION OF STUDY MEDICATION

A standard amount of study drug for the percent BSA under treatment will be measured and applied to the treatment area once daily to achieve a dose of approximately 8 mg/cm2, with each application administered approximately 24 hours apart. Study drug should only be administered to the treatment area, as directed by the Investigator, during the clinical trial.

The Target Efficacy Area used for the primary endpoint assessment in Part 1 will be based on one of the body sites as defined in the VIIS tool (upper back, upper arm or lower leg/shin) that has a VIIS scaling score of Grade 2 or higher as assessed by the Investigator. The body site with the worst VIIS scaling score should be selected, if applicable. The target efficacy area will be used for all efficacy analyses; for all other treated areas, data will be summarized.

Syneos Health #1009367

The Treatment Area will be determined by the Investigator as follows:

In Part 1, the initial treatment area will be defined as approximately 20% BSA with Grade 2 or higher on the VIIS scaling score, on one-half of the body, left or right side, and will include the target efficacy area. From Week 1 through Week 12, study drug will be applied in the initial treatment area.

If the Investigator determines that there are no safety or tolerability issues at the end of Week 12, the treatment area will increase to all of the affected areas of ichthyosis on one-half of the body (approximately 40-45% BSA in a typical SLS patient), left or right side. From Week 13 through Week 20, the study drug will be applied to the extended treatment area affected by ichthyosis.

If there are still no safety or tolerability issues at the end of Week 20, the treatment area will further increase to all affected areas of ichthyosis on the entire body (approximately 80-90% BSA in a typical SLS patient). From Week 21 through Week 24, the study drug will be applied to the entire body affected by ichthyosis.

For example, if the left lower leg is determined by the Investigator to be the target efficacy area, then the entire left leg would likely be defined as the initial treatment area. At the end of Week 12, if there are no safety or tolerability issues, the treatment area would extend to the entire left side of the body. At the end of Week 20, if there are no safety or tolerability issues, the treatment area would include the entire body.

Syneos Health #1009367

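### The Normal/Abnormal skin-exam summary in SAP 11.7 cannot register worsening in a treated region that is already coded Abnormal at baseline

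*SAP*

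**What the plan says.** On coding, SAP 11.7 says: "Body systems will be classified as 'Normal' or 'Abnormal' and abnormalities are described". On the summary, it says: "Dermatological examination findings will be fully summarized using the frequency and percentage of subjects under each classification for each body system". The tables are laid out by visit and treatment group, and overall. The protocol's safety section (10.5.1) likewise speaks only of the "normality of dermatological endpoints", and SAP 11 repeats the phrase.

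Other safety measures in the same SAP get more. SAP 11.3 gives laboratory values three-by-three shifts from baseline. For the ECG, SAP 11.5 says: "Shift tables for ECG result to each study visit on treatment will be provided". For the physical examination, SAP 11.6 tabulates findings "with an indication as to whether the finding is clinically significant". SAP 11.7 has none of these for the skin.

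On the skin being treated, protocol 4.1 requires: "Subject has active ichthyosis that is Grade 2 or higher on the VIIS scaling severity score". SAP 5.7 says that in Part 1 "the initial treatment area will be defined as approximately 20% BSA with Grade 2 or higher on the VIIS scaling score", on one side of the body. After Week 12, if there are no safety or tolerability issues, "the treatment area will increase to all of the affected areas of ichthyosis on one-half of the body". The last step, after Week 20, extends to affected skin on the whole body.

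**The concern.** Tolerability is a stated aim of both parts (protocol 3.1), and dermatological endpoints come first in the lists of safety measures (protocol 3.4.1 and 10.5.1; SAP 6.5). For a cream applied to diseased skin, the useful safety question is whether that skin became worse or developed something new. A two-level code with no baseline reference answers it only where the skin was normal to begin with.

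In treated regions the percentages are likely to sit at or near their ceiling in both arms at every visit. A reader of the Part 1 report could take identical columns as evidence of no local difference between drug and vehicle, when the table could not have shown one there.

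**Working it through.** The plan states no figure on this point, so there is none to reproduce. The check is a count, followed by a comparison of sections.

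**What the table can show.** Inputs: 6 drug and 3 vehicle subjects (protocol synopsis, Statistical Analysis) and two classes per region (SAP 11.7). Let *b* be the number of drug subjects coded Abnormal in a region at baseline. The largest number of Normal-to-Abnormal changes that the table can show is 6 − *b*.

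- *b* = 0 (a region normal in everyone): 6 − 0 = 6, so every new abnormality is visible.
- *b* = 3: 6 − 3 = 3.
- *b* = 6 (a region ichthyotic in everyone): 6 − 6 = 0.

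**Illustration, with assumed counts.** Take a treated region Abnormal at baseline in all subjects, and suppose that 3 of 6 drug subjects and 0 of 3 vehicle subjects develop a new reaction there.

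| Summary | Drug | Vehicle |
|---|---|---|
| SAP 11.7, baseline: Abnormal | 6/6 | 3/3 |
| SAP 11.7, after treatment: Abnormal | 6/6 | 3/3 |
| New or worsened from baseline | 3/6 (50%) | 0/3 (0%) |

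The SAP 11.7 rows would be the same if all 6 drug subjects had reacted.

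**Left and right.** SAP 11.7 lists back, arms and legs without side. SAP 5.7 confines treatment to one side until the end of Week 20. If the left leg is treated and the right is not, the legs row combines them, and the untreated leg alone can keep it Abnormal.

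**Where else a reaction could be seen in Part 1.** In the protocol's Table 1 the dermatologic exam falls at eight visits after baseline (Visits 2 to 9). Investigator VIIS falls at four of these (Visits 2, 5, 7 and 8). The other 8 − 4 = 4 are the home visits at Weeks 4, 8, 16 and 28, where photographs are taken only for a safety concern. The routine sources there are the dermatologic exam and adverse event collection.

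VIIS is scored at the upper back, upper arm, lower leg and dorsal foot (protocol 6.9). SAP 11.7 names nine regions besides Other. VIIS samples part of four of them (back, arms, legs, feet) and none of the other 9 − 4 = 5 (scalp, face, neck, chest and abdomen, hands), while treatment may reach 80-90% of body surface.

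**The case against.** The strongest reply is that local harm has other routes into the report.

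- **Adverse events.** Under protocol 9.1.1 to 9.1.2, an unfavourable sign is an adverse event, all adverse events must be recorded, a pre-existing condition is exempt only if it does not worsen, and an exacerbation after the first dose is treatment-emergent. A new irritant reaction on ichthyotic skin fits these definitions. Adverse events are collected at every visit, home visits included, and SAP 11 and 11.2 plan tables by term, severity and relationship. SAP 11.7 makes recording of clinically significant skin findings optional, but the SAP supersedes only the protocol's statistical methods (SAP 2).
- **VIIS erythema.** Change from baseline is summarised at each time point (SAP 10), by arm and with minimum and maximum (SAP 8.1). A maximum of +1 or more reveals that someone worsened. It does not say how many.
- **Text and review.** Abnormalities are described and the data listed, findings are to be medically evaluated, and narratives are planned.
- **Decisions.** The Investigator decides on area expansion subject by subject at Weeks 12 and 20, not from this table.

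All of this stands. A reader might infer from SAP 11.7 that the plan cannot show local harm at all, or that this is its main tolerability table. The documents support neither: they give the table no such rank, and the routes above exist.

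A reader might also infer that eligibility makes all nine subjects Abnormal in the treated row. That does not follow. The inclusion criterion names no body site, the target site may be back, arm or leg, and no single row is guaranteed to be full. Nor does the SAP say that known ichthyosis must be coded Abnormal. Regions typically spared, such as the face (protocol 1.1), can still show change.

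Finally, 3/6 versus 0/3 gives a Fisher exact p of about 0.46, so a better table would not separate the arms statistically. No safety testing is planned, and the gain is descriptive.

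**Conclusion.** The point holds for one supporting table. In any treated region coded Abnormal at baseline, the SAP 11.7 summary cannot record worsening or a new reaction, and the merging of sides blurs it further until the end of Week 20 in Part 1. The capacity lost in a region is *b* of 6 drug subjects, reaching 6 of 6 where all start Abnormal.

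This assumes that examiners code ichthyotic skin as Abnormal. The inference is strong but unstated. If coding is left to each site or home nurse, the percentages become hard to interpret for a different reason.

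The gap matters most at the four home visits and in regions that VIIS does not sample. This SAP covers Part 1 only. In Part 2 every dermatologic exam after baseline coincides with a VIIS assessment, so the timing gap closes there, but the limit to four body sites remains. The 3/6 versus 0/3 counts are an illustration, not an expected result. This is an inexpensive improvement worth making, not a failure of the safety plan.

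**What to change.** In SAP 11.7, add the number and percentage of subjects with a dermatologic finding new or worsened from baseline in treated regions, by arm and dosing period (the 20%, 40-45% and 80-90% periods already used in SAP 9.2.1). Assign each exam to a period by the area actually under treatment before it, and show Week 28 separately as follow-up. Derive the status from the abnormality descriptions, classified before unblinding, with unchanged baseline ichthyosis not counted. Include a clinical-significance indication as in SAP 11.6. State whether known ichthyosis is coded Abnormal.

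Add to the safety tables the number of subjects by arm with an increase of at least one grade from baseline in Investigator VIIS erythema at treated sites. The VIIS form already records left and right separately.

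Both tables use data already collected. The cost is SAP wording, two tables and a short blinded review of text for about nine subjects. The text is ungraded and comes partly from home nurses, so judging what has worsened carries some subjectivity. Writing the classification rule down before the review limits this.

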12. INTERIM ANALYSES

No interim analyses are planned for this clinical trial. The analysis at the end of Part 1 is a per-protocol planned analysis and will be fully unblinded.

Syneos Health #1009367

13. CHANGE FROM ANALYSIS PLANNED IN PROTOCOL

Analysis visit windows will not be applied given that the analysis visits are not going to be within the 3-5 days as stated in the protocol, instead the visits will be displayed as collected on the CRF.

Syneos Health #1009367

14. PROGRAMMING CONSIDERATIONS

14.1. GENERAL CONSIDERATIONS

- A separate SAS program will be created for each output.
- Each output will be stored in a separate file.
- Output files will be delivered in Word format and pdf format.
- Numbering of TFLs will follow ICH E3 guidance (or other logical order for *studies* performed according to GPP)

14.2. TABLE, LISTING, AND FIGURE FORMAT

14.2.1. General

- All TLFs will be produced in landscape format, unless otherwise specified.
- All TLFs will be produced using the Courier New font, size eight which is the smallest acceptable point size for the Regulatory Authorities.
- The data displays for all TLFs will have a minimum 1-inch margin on all four sides.
- Headers and footers for figures will be in Courier New font, size eight which is the smallest acceptable point size for the Regulatory Authorities.
- Legends will be used for all figures with more than one variable, group, or item displayed.
- TLFs will be in black and white (no color), unless otherwise specified
- Specialized text styles, such as bolding, italics, borders, shading, and superscripted and subscripted text, will not be used in the TLFs, unless otherwise specified. On some occasions, superscripts 1, 2, or 3 may be used (see below).
- Only standard keyboard characters will be used in the TLFs. Special characters, such as non-printable control characters, printer-specific, or font-specific characters, will not be used. Hexadecimal-derived characters will be used, where possible, if they are appropriate to help display math symbols (e.g., µ). Certain subscripts and superscripts (e.g., cm², C_{max}) will be employed on a case-by-case basis.
- Mixed case will be used for all titles, footnotes, column headers, and programmersupplied formats, as appropriate.

14.2.2. Headers

 All output should have the following header at the top left of each page: Aldeyra Protocol ADX-102-SLS-006 (Syneos Health study number 1009367) Draft/Final Run <date>

Syneos Health #1009367

- All output should have Page n of N at the top or bottom right corner of each page.
 TLFs should be internally paginated in relation to the total length (i.e., the page
 number should appear sequentially as page n of N, where N is the total number of
 pages in the table).
- The date output was generated should appear along with the program name as a footer on each page.

